## 11.1. Subject Information

Safety will be evaluated for all subjects who have received at least 1 dose of study drug (JNJ-63723283 or daratumumab) in any part of the study. The subjects in the Safety Run-in cohort may be included in the efficacy analyses and listed separately. The pharmacokinetic analyses will be performed on the population described in Section 11.4.

Part 2:

The primary analysis population for the efficacy endpoints will be the intent-to-treat (ITT) population, which will include all randomized subjects in Part 2.

Part 3:

The primary analysis population for the efficacy endpoints will be the ITT population, which will include all randomized subjects in Part 3.

# 11.2. Sample Size Determination

# Part 2:

Assuming the ORR for daratumumab monotherapy is approximately 30% and the addition of JNJ-63723283 improves ORR by 20%, approximately 80 subjects will be randomized in a 1:1 ratio to achieve at least 70% power with a 2-sided alpha of 0.20 to reject the null hypothesis that there is no difference in ORR between the 2 treatment arms.

# Part 3:

Assuming a median PFS of 4 months for the daratumumab monotherapy group (Lokhorst 2015; Lonial 2016) and a 33% reduction in risk of disease progression or death for the combination group (hazard ratio=0.67; median PFS=6 months), 230 PFS events are needed to achieve a power of 85% using a log-rank test with a 2-sided alpha of 0.05. With a 12-month accrual period and an additional 6-month follow-up, the sample size needed for the study is approximately 300 (150/treatment group) subjects.

Long-term survival follow-up will continue until 205 deaths have been observed. Therefore, Part 3 of this study will achieve approximately 80% power to detect a 33% reduction in the risk of death (hazard ratio=0.67) with a log-rank test (2-sided alpha=0.05).

# 11.3. Efficacy Analyses

Response to study treatment and progressive disease will be evaluated by a validated computer algorithm. Efficacy analyses will be performed separately for Part 2 and Part 3 of this study.

Part 2:

The primary endpoint, ORR, will be tabulated, and its two-sided 95% exact confidence interval will also be presented. For the calculation of ORR, those subjects who are not evaluable for response will be considered as non-responders In addition, the number and percentage of subjects in each response category will also be tabulated.

For time-to-event endpoints (PFS, OS, and duration of response), Kaplan-Meier estimates of the survival functions will be presented. For PFS and OS, treatment comparison will be made via a log-rank test. Cox's regression will be performed to obtain the hazard ratio estimate and the corresponding 95% CI, which will be used as a measure for treatment effect. Additional Cox's regression may be performed to include appropriate baseline prognostic variables.

Part 3:

For the primary endpoint of PFS, the primary analysis will consist of a stratified log-rank test for the comparison of the PFS distribution between the 2 treatment groups. The Kaplan-Meier method will be used to estimate the distribution of overall PFS for each treatment. The treatment effect (hazard ratio) and its two-sided 95% confidence intervals are to be estimated using a stratified Cox regression model with treatment as the sole explanatory variable.

Duration of response will be provided descriptively using the Kaplan-Meier method without formal statistical comparison. Other time-to-event efficacy endpoints will be analyzed similarly.

Comparison between the 2 treatment groups for ORR and other binary endpoints will be conducted using the stratified Cochran-Mantel-Haenszel test. The Mantel-Haenszel odds ratio will be provided along with its two-sided 95% confidence interval.

A multiplicity adjustment strategy will be implemented to control the overall family wise type I error rate for the Phase 3 part of this study. Additional details will be provided in the Statistical Analysis Plan.

# 11.4. Pharmacokinetic Analyses

Pharmacokinetic analyses will be performed on the PK-evaluable population, defined as subjects who have received at least 1 dose of daratumumab or JNJ-63723283 and have at least 1 postinfusion sample.

All concentrations below the lowest quantifiable concentration or missing data will be labeled as such in the concentration database. Concentrations below the lowest quantifiable concentration will be treated as zero in the summary statistics. The number of subjects and samples excluded from the analysis will be clearly documented in the Clinical Study Report.

Descriptive statistics will be used to summarize daratumumab and JNJ-63723283 serum concentrations at each sampling time point.  $C_{min}$  is defined as the minimal concentration observed immediately before infusion and  $C_{max}$  is defined as the maximum concentration observed at the end of infusion, as presented in the summary of serum concentration by sampling time point. Other PK parameters, if available, may also be summarized.

If sufficient data are available, population-PK analysis of serum concentration-time data of daratumumab or JNJ-63723283 may be performed and may be combined with data from other studies. If the population-PK analysis is conducted, details will be given in a population-PK analysis plan and the results of the analysis will be presented in a separate report.

# 11.5. Immunogenicity Analyses

The incidence of anti-JNJ-63723283 and anti-daratumumab antibodies will be summarized for all subjects who receive at least 1 dose of JNJ-63723283 and daratumumab and have appropriate serum samples for detection of antibodies to JNJ-63723283 and daratumumab (ie, subjects with at least 1 sample obtained after their first dose). In addition, subjects who are positive for antibodies to JNJ-63723283 or daratumumab will be listed.

Other immunogenicity analyses may be performed to further characterize the immune responses that are generated.

# 11.6. Biomarker Analyses

Biomarker analyses will be stratified by clinical covariates or molecular subgroups using the appropriate statistical methods (eg, parametric or non-parametric, univariate or multivariate,

analysis of variance, or survival analysis, depending on the endpoint). Correlation of baseline expression levels or changes in expression levels with response to time-to-event endpoints will identify responsive (or resistant) subgroups in addition to genes and pathways attenuated following treatment with daratumumab.

Any pharmacodynamic measures will be listed, tabulated, and where appropriate, plotted. Subjects may be grouped by cohort, dose schedule, or clinical response. Results of biomarker and pharmacodynamic analyses may be presented in a separate report. Planned analyses are based on the availability of clinically valid assays and may be deferred if emerging study data show no likelihood of providing useful scientific information.

# 11.7. Pharmacokinetic/Pharmacodynamic Analyses

If sufficient data are available, then other pharmacokinetic/pharmacodynamic modeling may be performed, including exploring the relationship between serum concentrations of daratumumab and/or JNJ-63723283 and endpoints of clinical efficacy and safety. If performed, details and results of the analysis will be presented in a separate report.

# 11.8. Patient-reported Outcomes Analyses (Part 3)

The EORTC-QLQ-C30 scale scores, EQ-5D-5L utility value, and EQ-5D-5L VAS will be summarized at each timepoint, by treatment arm. Within-group and between-group treatment effect on the PRO endpoints will be assessed by change from baseline using mixed models for repeated measures.

# 11.9. Medical Resource Utilization Analyses (Part 3)

Medical resource utilization will be descriptively summarized by treatment group. Additional analyses may be conducted; details and results of any additional analyses will be presented in a separate report.

## 11.10. Safety Analyses

Safety data from each part of this study may be combined as deemed appropriate.

## **Adverse Events**

The verbatim terms used in the CRF by investigators to identify adverse events will be coded using the Medical Dictionary for Regulatory Activities (MedDRA). Treatment-emergent adverse events are adverse events with onset during the treatment phase or that are a consequence of a pre-existing condition that has worsened since baseline. All reported adverse events will be included in the analysis. For each adverse event, the percentage of subjects who experience at least 1 occurrence of the given event will be summarized by treatment group. In addition, comparisons between treatment groups will be provided if appropriate.

Summaries, listings, datasets, or subject narratives may be provided, as appropriate, for those subjects who die, who discontinue treatment due to an adverse event, or who experience a severe or a serious adverse event.

# **Clinical Laboratory Tests**

Laboratory data will be summarized by type of laboratory test. Reference ranges and markedly abnormal results (specified in the Statistical Analysis Plan) will be used in the summary of laboratory data. Descriptive statistics will be calculated for each laboratory analyte at baseline and for observed values and changes from baseline at each scheduled timepoint. Changes from baseline results will be presented in pre- versus posttreatment cross-tabulations (with classes for below, within, and above normal ranges). A listing of subjects with any laboratory results outside the reference ranges will be provided. A listing of subjects with any markedly abnormal laboratory results will also be provided.

Parameters with predefined NCI-CTCAE toxicity grades will be summarized. Change from baseline to the worst adverse event grade experienced by the subject during the study will be provided as shift tables.

## Electrocardiogram

Electrocardiogram data will be summarized based on categories of normal, abnormal either clinically significant or not clinically significant and listed.

## Vital Signs

Descriptive statistics of temperature, pulse/heart rate, and blood pressure (systolic and diastolic) values and changes from baseline will be summarized at each scheduled timepoint. The percentage of subjects with values beyond clinically important limits will be summarized.

## 11.11. Interim Analyses for Part 3

For PFS, one interim analysis is planned. The interim analysis will be performed when 138 PFS events, which is 60% of the total planned PFS events, have been accumulated. The purpose of this interim analysis is to evaluate interim efficacy data. The significance level at this interim analysis will be calculated based on the observed number of PFS events at the interim analysis, using the O'Brien-Fleming boundaries as implemented by the Lan-DeMets alpha spending method. Assuming 138 (60%) PFS events are observed, the alpha to be spent in this interim analysis will be 0.00762 2-sided). If the observed PFS hazard ratio is greater than 1, favoring the daratumumab group, the study may be terminated for futility.

For OS, 2 interim analyses are planned. The timing of these analyses corresponds to that of PFS interim and final analyses, respectively; the final OS analysis will occur after 205 deaths have been observed. At the first interim analysis, an alpha of 0.0001 will be spent. For the second interim analysis and final analysis, the alpha to be spent will be determined by a linear alpha spending function based on the observed number of deaths at that time, ie, the cumulative alpha to be spent will be the total alpha (0.05) multiplied by the proportion of the observed number of deaths out of the total planned number of deaths (205). It is noted that, even if the significance of PFS has already been established, testing of OS may continue as planned until a definitive conclusion on OS is reached.

## **11.12.** Statistical Methods Effective Protocol Amendment 2

As of 25 May 2018, the Sponsor terminated further enrollment into this study and subjects continuing study will receive daratumumab monotherapy. Since the total number of subjects treated in this study is small, no formal statistical hypothesis testing will be performed. A descriptive data summary will be provided only for all subjects who received study medication. Subject information will be summarized or listed for all treated subjects. Subject narratives may be provided, as appropriate. Safety assessment data (AEs, Laboratory values, vital signs etc.) will be listed for each subject.

# 12. ADVERSE EVENT REPORTING

Timely, accurate, and complete reporting and analysis of safety information from clinical studies are crucial for the protection of subjects, investigators, and the Sponsor, and are mandated by regulatory agencies worldwide. The Sponsor has established Standard Operating Procedures in conformity with regulatory requirements worldwide to ensure appropriate reporting of safety information; all clinical studies conducted by the Sponsor or its affiliates will be conducted in accordance with those procedures.

#### Method of Detecting Adverse Events and Serious Adverse Events

Care will be taken not to introduce bias when detecting adverse events or serious adverse events. Open-ended and nonleading verbal questioning of the subject is the preferred method to inquire about adverse event occurrence.

## 12.1. Definitions

## 12.1.1. Adverse Event Definitions and Classifications

#### **Adverse Event**

An adverse event is any untoward medical occurrence in a clinical study subject administered a medicinal (investigational or non-investigational) product. An adverse event does not necessarily have a causal relationship with the treatment. An adverse event can therefore be any unfavorable and unintended sign (including an abnormal finding), symptom, or disease temporally associated with the use of a medicinal (investigational or non-investigational) product, whether or not related to that medicinal (investigational or non-investigational) product. (Definition per International Council on Harmonisation [ICH]).

This includes any occurrence that is new in onset or aggravated in severity or frequency from the baseline condition, or abnormal results of diagnostic procedures, including laboratory test abnormalities.

Note: The Sponsor collects adverse events starting with the signing of the ICF (refer to Section 12.3.1, All Adverse Events, for time of last adverse event recording).

#### Serious Adverse Event

A serious adverse event based on ICH and EU Guidelines on Pharmacovigilance for Medicinal Products for Human Use is any untoward medical occurrence that at any dose:

- Results in death
- Is life-threatening (The subject was at risk of death at the time of the event. It does not refer to an event that hypothetically might have caused death if it were more severe.)
- Requires inpatient hospitalization or prolongation of existing hospitalization
- Results in persistent or significant disability/incapacity
- Is a congenital anomaly/birth defect
- Is a suspected transmission of any infectious agent via a medicinal product
- Is Medically Important\*

\*Medical and scientific judgment should be exercised in deciding whether expedited reporting is also appropriate in other situations, such as important medical events that may not be immediately life threatening or result in death or hospitalization but may jeopardize the subject or may require intervention to prevent one of the other outcomes listed in the definition above. These should usually be considered serious.

If a serious and unexpected adverse event occurs for which there is evidence suggesting a causal relationship between the study drug and the event (eg, death from anaphylaxis), the event must be reported as a serious and unexpected suspected adverse reaction even if it is a component of the study endpoint (eg, all-cause mortality).

#### Unlisted (Unexpected) Adverse Event/Reference Safety Information

An adverse event is considered unlisted if the nature or severity is not consistent with the applicable product reference safety information. For JNJ-63723283 and daratumumab, the expectedness of an adverse event will be determined by whether or not it is listed within the Reference Safety Information in the Investigator's Brochures.

#### Adverse Event Associated With the Use of the Drug

An adverse event is considered associated with the use of the drug if the attribution is possible, probable, or very likely by the definitions listed in Section 12.1.2, Attribution Definitions.

## 12.1.2. Attribution Definitions

#### Not Related

An adverse event that is not related to the use of the drug.

## Doubtful

An adverse event for which an alternative explanation is more likely, eg, concomitant drug(s), concomitant disease(s), or the relationship in time suggests that a causal relationship is unlikely.

## Possible

An adverse event that might be due to the use of the drug. An alternative explanation, eg, concomitant drug(s), concomitant disease(s), is inconclusive. The relationship in time is reasonable; therefore, the causal relationship cannot be excluded.

# Probable

An adverse event that might be due to the use of the drug. The relationship in time is suggestive (eg, confirmed by dechallenge). An alternative explanation is less likely, eg, concomitant drug(s), concomitant disease(s).

# Very Likely

An adverse event that is listed as a possible adverse reaction and cannot be reasonably explained by an alternative explanation, eg, concomitant drug(s), concomitant disease(s). The relationship in time is very suggestive (eg, it is confirmed by dechallenge and rechallenge).

# 12.1.3. Severity Criteria

The severity assessment for an adverse event or serious adverse event should be completed using the NCI-CTCAE Version 4.03 Any adverse event or serious adverse event not listed in the NCI-CTCAE Version 4.03 will be graded according to investigator clinical judgment by using the standard grades as follows:

Grade 1 (Mild): Awareness of symptoms that are easily tolerated, causing minimal discomfort and not interfering with everyday activities

Grade 2 (Moderate): Sufficient discomfort is present to cause interference with normal activity

Grade 3 (Severe): Extreme distress, causing significant impairment of functioning or incapacitation. Prevents normal everyday activities

Grade 4: Life-threatening or disabling adverse event

Grade 5: Death related to the adverse event

The investigator should use clinical judgment in assessing the severity of events not directly experienced by the subject (eg, laboratory abnormalities).

# 12.2. Special Reporting Situations

Safety events of interest on a Sponsor study drug that may require expedited reporting or safety evaluation include, but are not limited to:

- Overdose of a Sponsor study drug
- Suspected abuse/misuse of a Sponsor study drug
- Accidental or occupational exposure to a Sponsor study drug
- Medication error involving a Sponsor product (with or without subject/patient exposure to the Sponsor study drug, eg, name confusion)
- Exposure to a Sponsor study drug from breastfeeding

Special reporting situations should be recorded in the CRF. Any special reporting situation that meets the criteria of a serious adverse event should be recorded on the serious adverse event page of the CRF.

## 12.3. Procedures

#### 12.3.1. All Adverse Events

All adverse events and special reporting situations will be reported from the time a signed and dated ICF is obtained until 30 days after the last dose of study drug, or until start of subsequent anticancer therapy or the subject withdraws consent for study participation, if earlier, which may include contact for follow-up of safety. For subjects who have received subsequent treatment with therapeutic intent for multiple myeloma during the adverse event reporting period, only adverse events that are considered to be possibly, probably, or definitely related to JNJ-63723283 or daratumumab need to be reported. Serious adverse events, including those spontaneously reported to the investigator, must be reported using the Serious Adverse Event Form. Serious adverse events considered by the investigator to be related to JNJ-63723283 or daratumumab should continue to be reported during the follow-up period. The Sponsor will evaluate any safety information that is spontaneously reported by an investigator beyond the time frame specified in the protocol.

Disease progression should not be recorded as an adverse event or serious adverse event term; instead, clinical sequelae resulting from disease progression/lack of efficacy will be reported if they fulfill the serious adverse event definition (refer to Section 12.1.1). Death should not be recorded as an adverse event or serious adverse event, but as the outcome of an adverse event. The adverse event that resulted in the death should be reported as a serious adverse event. All events that meet the definition of a serious adverse event will be reported as serious adverse events, regardless of whether they are protocol-specific assessments. Anticipated events will be recorded and reported as described in Attachment 9.

All adverse events, regardless of seriousness, severity, or presumed relationship to study drug, must be recorded using medical terminology in the source document and the CRF. Whenever possible, diagnoses should be given when signs and symptoms are due to a common etiology (eg, cough, runny nose, sneezing, sore throat, and head congestion should be reported as "upper respiratory infection"). Investigators must record in the CRF their opinion concerning the relationship of the adverse event to study therapy. All measures required for adverse event management must be recorded in the source document and reported according to Sponsor instructions.

The Sponsor assumes responsibility for appropriate reporting of adverse events to the regulatory authorities. The Sponsor will also report to the investigator (and the head of the investigational institute where required) all suspected unexpected serious adverse reactions (SUSARs). For anticipated events reported as individual serious adverse events the Sponsor will make a determination of relatedness in addition to and independent of the investigator's assessment. The Sponsor will periodically evaluate the accumulating data and, when there is sufficient evidence and the Sponsor has determined there is a reasonable possibility that the drug caused a serious anticipated event, they will submit a safety report in narrative format to the investigators (and the head of the institute).

The investigator (or Sponsor where required) must report SUSARs to the appropriate Independent Ethics Committee/Institutional Review Board (IEC/IRB) that approved the protocol unless otherwise required and documented by the IEC/IRB.

Subjects (or their designees, if appropriate) will be provided with a "wallet (study) card" and instructed to carry this card with them for the duration of the study indicating the following:

- Study number
- Statement, in the local language(s), that the subject is participating in a clinical study
- Investigator's name and 24-hour contact telephone number
- Local Sponsor's name and 24-hour contact telephone number (for medical staff only)
- Site number
- Subject number
- Blood type and IAT (as described in Section 9.7)

# 12.3.1.1. Daratumumab Monotherapy Period

Non-serious adverse events will not be reported during the daratumumab monotherapy period. However, SAEs (including SPMs) must be reported continuously from time of ICF until EOT Visit or until the subject withdraws consent for study participation or until the subject starts subsequent anticancer therapy whichever occurs first. Beyond the EOT Visit reporting period after the last dose of study medication, information on SAEs, including SPMs, considered possibly, probably or definitely related to study drug will continue to be collected.

Serious Adverse Event reporting after the final database lock, established once Protocol Amendment 2 is implemented at all sites, will be limited to SAE reporting into the Sponsor's global safety database, using SAE Form (paper form) faxed to Sponsor's Local Operational Company/Local Safety Officer.

SAEs (see Section 12.3.2) should include information on study agent administration and concomitant medications associated with an SAE.

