## **End-of-Treatment Visit**

Unless a subject withdraws consent for study participation or is lost to follow up, an End-of-Treatment Visit is to occur 4 weeks ( $\pm$ 7 days) after the last dose of study treatment. Every effort should be made to conduct the End-of-Treatment Visit before the subject starts subsequent treatment. If a subject is unable to return to the site for the End-of-Treatment Visit, then the subject should be contacted to collect information on adverse events and concomitant medications used to treat adverse events as specified in Section 12.3.1. If the End-of-Treatment visit occurs before 30 days, then the subject should be contacted after 30 days so that all adverse events that occurred within the 30-day period are recorded. Additional information on reporting of adverse events is presented in Section 12.

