## 9.1.4. Follow-Up Phase

Each subject is to have a follow-up visit 8 weeks after the last dose of study treatment. Beyond the Week 4 End-of-Treatment Visit, information on serious adverse events considered related to study treatment will continue to be collected. For a subject who discontinues study treatment before disease progression, disease evaluations should continue to be performed as specified in the Time and Events Schedule. After disease progression is documented, subsequent anticancer treatment, response to subsequent treatment, and date of progression will be recorded and survival status will be obtained. If the information is obtained via telephone contact, then written documentation of the communication must be available for review in the source documents. If the subject has died, then the date and cause of death will be collected and documented on the eCRF.

During the Daratumumab Monotherapy Period, SAEs (including SPMs) must be reported continuously from time of ICF until EOT Visit or until the subject withdraws consent for study participation or until the subject starts subsequent anticancer therapy whichever occurs first. Beyond the EOT Visit reporting period after the last dose of study medication, information on

SAEs, including SPMs, considered possibly, probably or definitely related to study drug will continue to be collected.

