# Table 24: Time and Events Schedule – Daratumumab Monotherapy Period for Subjects No Longer Receiving JNJ-63723283 in Combination with Daratumumab

		Cycles	s 1 and	2	Cycle	s 3 to 6	Cycles 7+	EOT a	
Study Day	1	8	15	22	1	15	1	Post-Treatment Week 4 (±7 days)	
Procedures/Assessments Study procedures									
Informed consent	Subj	ects m	ust sign	the info				-specific procedures are performed.	
Physical Examination		-	-		Symp	tom-direct	ted physical exai	nination only	
Dosing									
Daratumumab 16 mg/kg dosing (IV)	Х	Х	Х	Х	Х	Х	Х		
Preinfusion and postinfusion medications b	Х	Х	Х	Х	Х	Х	Х		
Weight	Х				Х		Х	Х	
Vital Signs (immediately before start and at end of each daratumumab infusion)	Х	Х	Х	X	Х	X	Х	Х	
Laboratory Assessments c									
Urine or serum pregnancy test (women of childbearing potential only)				•		Only if	f clinically indica	ated.	
Biochemistry	Х				Х		Х	Х	
Hematology	Х	Х	Х	Х	Х	Х	Х	Х	
Investigator assessment of response c		•	•	.			• •		
SPEP and 24-hour UPEP d , Serum calcium corrected for albumin d , Serum FLC & serum/urine immunofixation d , Bone marrow aspirate/bone marrow biopsy Skeletal survey/Assessment of lytic bone disease	As	s clinic						standard of care until PD maging (X-ray, CT, or MRI may be used)	
Assess extramedullary plasmacytomas						As per	local standard of	care	
Ongoing Subject Review						1.5 per			
SAEs, including SPMs	Continuous from time of ICF until EOT Visit or until the subject withdraws consent for study participation or until the subject starts subsequent anticancer therapy e whichever occurs first. Beyond the EOT Visit reporting period after the last dose of study medication, information on SAEs, including SPMs, considered possibly, probably or definitely related to study drug will continue to be collected.								

- a) To occur 4 weeks (±7 days) after the last dose of study drug or as soon as possible before the start of subsequent therapy.
   b) Refer to Section 6.4.1.2 and Section 6.4.1.3 for additional information.
- c) Evaluations will be conducted at the local laboratory and responses will be interpreted by the investigator.

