### 5. NARRATIVE CRITERION

- Deaths within 30 days of last dose of study treatment
- Discontinuations of study treatment due to treatment-emergent AEs
- Treatment-emergent serious AEs
- Adverse events of clinical interest
  - Infusion-related reaction, Grade 3 or higher
  - Treatment-emergent Immune-related AE, Grade 3 or higher
  - Treatment-emergent infections/infestations, SAE or Grade 3 or higher
  - Treatment-emergent hemorrhage events, SAE or Grade 3 or higher
  - Treatment-emergent tumor lysis syndrome, SAE or Grade 3 or higher
  - New Malignancies
  - Treatment-emergent anaphylaxis or suspected anaphylaxis
- Treatment-emergent for subject who require the DIRA test result to confirm CR/sCR or treatment-emergent for subject who has earlier date of CR/sCR due to DIRA
- Treatment-emergent intravascular hemolysis
- Treatment-emergent interference with cross-matching and red blood cell antibody screening

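### In the daratumumab monotherapy period, SAE reporting regardless of causality ends at an EOT Visit that may fall on day 21, while Table 1, 9.1.3 and 12.3.1 run to day 30 after the last dose

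*Protocol*

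**What the plan says.** **Monotherapy rule.** Protocol 12.3.1.1 ends SAE reporting regardless of causality at the EOT Visit: SAEs "must be reported continuously from time of ICF until EOT Visit", or until consent withdrawal or subsequent anticancer therapy if either comes first. Section 9.1.4 repeats it ("SAEs (including SPMs) must be reported continuously from time of ICF until EOT Visit"), as does the SAE row of Table 24 ("Continuous from time of ICF until EOT Visit or until the subject withdraws consent for study participation"). After the visit, only SAEs and second primary malignancies "considered possibly, probably or definitely related to study drug will continue to be collected".

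**Timing of the visit.** Table 24, footnote a: "To occur 4 weeks (±7 days) after the last dose of study drug or as soon as possible before the start of subsequent therapy". Under 10.1.1 the subject leaves the study once that visit is complete.

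**Rule elsewhere.** Section 12.3.1, the parent of 12.3.1.1, collects adverse events "until 30 days after the last dose of study drug", cut short by subsequent therapy or consent withdrawal. The adverse event row of Table 1 gives the same 30 days and makes it independent of the EOT date. Section 9.1.3 adds a safeguard: "If the End-of-Treatment visit occurs before 30 days, then the subject should be contacted after 30 days".

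**SAP.** Section 5 lists "Deaths within 30 days of last dose of study treatment" as a trigger for a narrative.

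**The concern.** The main protocol separates the safety window from the visit date. The monotherapy text joins them again, so the period in which every SAE must be reported depends on when a visit with a two-week window happens to be scheduled. If the visit is early, an SAE before day 30 reaches the sponsor only if the investigator considers it related.

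This matters for three reasons:

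- SAEs are the one data stream kept for this period. Section 12.3.1.1 drops non-serious events and 17.5 stops eCRF entry, so nothing else would show the event.
- Under 12.3.1 a death is recorded as the outcome of an adverse event. Table 24 has no survival contact after EOT. A fatal event judged unrelated between the visit and day 30 therefore has no required route into the data.
- For anticipated events reported as SAEs, such as infection, bleeding or renal failure, 12.3.1 has the sponsor judge relatedness independently of the investigator, and Attachment 9 provides for aggregate review. An event left unreported because the investigator called it unrelated reaches neither check.

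**Working it through.** **Inputs.** EOT Visit at 4 weeks ±7 days after the last dose (Table 24, footnote a). Comparison window of 30 days after the last dose (12.3.1, Table 1, 9.1.3). The plan states no figure for the shortfall, so there is none to reproduce.

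**Range of visit dates.** 4 × 7 = 28 days. 28 − 7 = 21 and 28 + 7 = 35, so the visit may fall on any of 15 dates, day 21 to day 35.

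**Formulas**, for a visit on day *d* with no new therapy or consent withdrawal before day 30:

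- Shortfall against 30 days = max(0, 30 − *d*)
- Excess over 30 days = max(0, *d* − 30)

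| EOT on day | Shortfall (days) | Share of 30 days | Excess (days) |
|---|---|---|---|
| 21 | 30 − 21 = 9 | 9/30 = 30% | 0 |
| 28 (nominal) | 30 − 28 = 2 | 2/30 = 7% | 0 |
| 30 | 0 | 0% | 0 |
| 31 | 0 | 0% | 1 |
| 35 | 0 | 0% | 5 |

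A visit held exactly on schedule already stops 2 days short. The shortfall arises on days 21 to 29, which are 9 of the 15 permitted dates. The documents do not say how visits will be spread over the window, so no average shortfall is given.

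**Visit moved ahead of new therapy.** Footnote a allows an earlier visit when subsequent therapy is about to start. The 12.3.1 window also ends when that therapy starts, so this adds little or nothing to the gap.

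**Does the 9.1.3 contact close the gap?** The two readings are:

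- *It applies:* it stands in the general EOT text, and no passage switches it off.
- *It does not apply:* 9.1.1.1 sends monotherapy subjects to Table 24, which has no such contact. Section 10.1.1 ends their participation at the visit, and 12.3.1.1 requires no report of an unrelated SAE after it.

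The text supports both readings, so a site cannot tell which to follow.

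**The case against.** The strongest answer is that the narrower rule is deliberate. It is worded alike in three places, and Amendment 2 openly reduces data collection for this period. Daratumumab alone is approved for this population (1.3), the PD-1 antibody has been stopped, few subjects were treated, and no hypothesis is tested (11.12). Related SAEs are still collected after the visit, and the sponsor evaluates spontaneous reports beyond the stated time frame (12.3.1). Reduced collection does explain dropping non-serious events. It does not explain why the SAE window should vary between subjects by up to two weeks, and no reason is given.

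Other parts of the objection stand, and they limit the point:

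- The main protocol is not uniform. The general text of 9.1.4 also restricts collection to related SAEs after the Week 4 EOT Visit. The conflict is with Table 1, 9.1.3 and 12.3.1, and dependence on a causality call after the window is not peculiar to the monotherapy period.
- A reader might infer that unrelated late events will be lost. The documents do not show that, because the 9.1.3 contact is never withdrawn. Amendment 2 edited that very paragraph to add the ±7 days and left the contact in place. What can be said is that 12.3.1.1 does not require such events to be reported.
- A reader might also infer that the SAP demands 30 days of SAE reporting. Its Section 5 is a narrative trigger for deaths and sets no reporting window. The SAP analysis follows the final database lock (SAP Section 1), and eCRF entry stops at each site when Amendment 2 is implemented (17.5). Later monotherapy deaths fall outside that analysis whatever the EOT date. The mismatch concerns only subjects whose last dose is near or before the lock.
- The early deaths that led to the stop were seen with daratumumab plus atezolizumab in lung cancer (1.4). They give a reason for care with deaths in this study, but are not evidence about daratumumab alone.

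**Conclusion.** The inconsistency is real and bounded, and it should be corrected. As written, the monotherapy rule leaves up to 9 days, and 2 days at the nominal visit date, in which SAEs judged unrelated, fatal ones included, need not be reported, although Table 1, 9.1.3 and 12.3.1 would cover those days. From day 30 there is no shortfall, and a visit on days 31 to 35 gives 1 to 5 days more than the 30-day rule.

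The size rests on two assumptions: that the visit takes place within its stated window, and that neither new therapy nor consent withdrawal ends reporting first. Whether events would go unreported in practice depends on how sites read 9.1.3, which the protocol leaves open. The conclusion does not depend on the SAP.

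**What to change.** In 12.3.1.1, in the monotherapy paragraph of 9.1.4 and in the SAE row of Table 24, move the end of SAE reporting regardless of causality from the EOT Visit to day 30 after the last dose or the EOT Visit, whichever is later. Keep the existing end conditions of consent withdrawal and subsequent anticancer therapy. State in the same places that the 9.1.3 contact after day 30 applies when the visit is earlier, and add it to Table 24.

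Taking the later of the two dates matters. A flat 30-day limit would drop unrelated SAEs on days 31 to 35 that are reportable now when the visit is late.

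The cost is wording in three places and one phone contact for each subject whose EOT Visit falls before day 30, a step that 9.1.3 already describes. No visit or sample is added.
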